2.2 Pharmaceutical Data durvalumab

Supplied as a vial liquid solution containing 500 mg (nominal) durvalumab. The solution contains 50 mg/mL durvalumab, 26 mM histidine/histidine-HCl, 275 mM trehalose dihydrate, 0.02% (w/v) polysorbate 80, at pH 6.0.

Stability:

The shelf life of durvalumab will be indicated on the vial label. Durvalumab must be used within the individually assigned expiry date on the label.

Storage:

durvalumab must be stored at 2°C to 8°C.

It is recommended that durvalumab is stored in opaque containers during storage to prevent excessive exposure to light.

Solution Preparation:

The dose of investigational product for administration must be prepared using aseptic technique. Total in-use storage time from needle puncture of durvalumab vial to the start of administration should not exceed 4 hours at room temperature or 24 hours at 2 to 8°C (36 to 46°F). If in-use storage time exceeds these limits, a new dose must be prepared from new vials. durvalumab does not contain preservatives and any unused portion must be discarded.

No incompatibilities have been observed between durvalumab and polyethylene, polypropylene, polyvinylchloride (PVC), or polyolefin copolymers. Saline bags must be latex free.

Doses will be administered using a 250 mL IV bag of normal saline (0.9% (weight/volume) sodium chloride injection) and delivered through an IV administration set with a 0.2- μ m in-line filter via an infusion pump into a peripheral vein.

Patient weight at baseline should be used for dosing calculations in patients ≤ 30 kg unless there is a $\geq 10\%$ change in weight. Dosing day weight can be used for dosing calculations instead of baseline weight per institutional standard.

For patients < 30 kg, calculate the dose volume of durvalumab and number of vials needed for the subject to achieve the accurate dose according to Appendix VI.

Patient weight at baseline should be used for dosing calculations unless there is a $\geq 10\%$ change in weight. An additional volume of 0.9% (weight/volume) saline equal to the calculated volume of durvalumab to be added to the IV bag must be removed from the bag prior to addition of durvalumab. The calculated volume of durvalumab is then added to the IV bag, and the bag is mixed by gentle inversion to ensure homogeneity of the dose in the bag. Infusion solutions must be allowed to equilibrate to room temperature prior to commencement of administration.

Route of Administration:

Intravenous.

Following preparation of durvalumab the entire contents of the IV bag should be administered as an IV infusion over approximately 60 minutes (± 5 minutes), using a 0.2- μ m in-line filter. The IV line will be flushed with a volume of normal saline equal to the priming volume of the infusion set used after the contents of the IV bag are fully administered, or complete the infusion according to institutional policy to ensure the full dose is administered and document if the line was not flushed.

2.3 Justification of durvalumab Dose/s, Schedule and Duration of Administration

The optimal duration of an immunotherapy used as neoadjuvant therapy to improve complete resection of the tumour is unknown.

For this trial, to minimize the delay for surgery, durvalumab will be administered at a dose of 750 mg for 3 planned doses, every 2 weeks for one month. Only early NSCLC will be included Stage IB (only T = 4 cm in greatest dimension, N0), Stage IIA (T2b,N0) and some of Stage IIB : (T1-2,N1) and (T3 : > 5 cm and ≤ 7 cm in greatest dimension surrounded by lung or associated with separate tumor nodule(s) in the same lobe but **without** mediastinum or chest wall involvements, or superior sulcus tumors, N0) on the basis of clinical evaluation (8th classification TNM, UICC 2015).

3 OBJECTIVES

3.1 Primary Objective

To assess the impact of neo-adjuvant therapy with durvalumab given by intravenous infusion for one month on the complete resection (see section 10).

3.2 Secondary Objectives

- Tolerance, adverse effects and tolerability of durvalumab.
- Delay between start of treatment and surgery.
- Response Rate (RECIST 1.1).
- Metabolic response rate on TEP-FDG on pre-treatment PET-CT and pre-operative PET-CT after 3 durvalumab infusions, on both primary tumor and eventual nodes.
- Post-operative adverse events (AE).
- Pathological response (as assessed by microscopic histological examination, with at least one slide assessed by cm of tumor in the greatest diameter, *i.e.* 5 to 30 slides assessed). Major Pathological Response on surgical tissue (tumor + nodes) as centrally reviewed by a panel of IFCT Pathologists, on both tumor and resected nodes, and defined as semi-quantitative evaluation of less than 10% or remaining tumor cells, in surgical primary tumor and nodes samples.
- Disease Free Survival (DFS)
- Overall survival (OS)

3.3 Exploratory objective

- Evaluation of predictive/prognostic significance of PD-1/PD-L1 expression (using at least SP263 antibody) on both pre-operative and surgical samples, and both tumor and infiltrating immune cells
- Evaluation of changes in plasma/serum cytokines and other biomarkers before and after treatment
- Characterization of the immune reactivity of tumors
- Analysis of the intestinal microbiome

4 TRIAL DESIGN

This is a multi-centre, prospective, single-arm phase II trial of the human monoclonal antibody directed against programmed cell death ligand-1 (PD-L1) durvalumab in neoadjuvant treatment in primary resectable stage IB (only T = 4 cm in greatest dimension, N0), stage IIA (T2b,N0) and some of stage IIB : (T1-2,N1) and (T3 : > 5 cm and ≤ 7 cm in greatest dimension surrounded by lung or associated with separate tumor nodule(s) in the same lobe but **without** mediastinum or chest wall involvements, or superior sulcus tumors, N0) non-small cell lung cancer patients.

Stage IB/IIA and some of stage IIB NSCLC
 
ECOG PS 0 or 1
 
age ≥ 18 years
 
pre-therapeutic tissue required
	I			
	N			
	C			
	L		Anti-PD-L1	Surgery
	U		durvalumab	between 2 days and 2 weeks after last infusion
	S	→	750 mg IV*	
	I		Day1, 15, 29	Surgical snap-frozen ¹ tissue(tumor+nodes) required
	O			
	N			
				Follow up for disease status and survival

4 weeks, 6 months and one year after surgery

Planned Sample Size: 81 patients
20 centres

* 10 mg/kg for patient weighting less than 30 kg (see appendix VI).

1. Optional

5 STUDY POPULATION

This trial will study patients with clinically Stage IB (only T = 4 cm in greatest dimension, N0), Stage IIA (T2b,N0) and some of Stage IIB : (T1-2,N1) and (T3 : > 5 cm and ≤ 7 cm in greatest dimension surrounded by lung or associated with separate tumor nodule(s) in the same lobe but **without** mediastinum or chest wall involvements, or superior sulcus tumors, N0) non-small cell lung cancer (NSCLC). Staging will be according to the TNM staging system for lung cancer (8th edition).

5.1 Eligibility Criteria

There will be NO EXCEPTIONS to eligibility requirements at the time of inclusion. Questions about eligibility criteria should be addressed prior to inclusion.

The eligibility criteria for this study have been carefully considered. Eligibility criteria are standards used to ensure that patients who enter this study are medically appropriate candidates for this therapy.

Patients must fulfil all of the following criteria to be eligible for admission to the study:

- 1 Histologically confirmed diagnosis of primary non-small cell carcinoma of the lung.
- 2 Tissue block of diagnosis must be available for submission after inclusion (one HES slide and one paraffin embedded block).
- 3 Patients must be classified clinically as Stage IB (only T = 4 cm in greatest dimension, N0), Stage IIA (T2b,N0) and some of Stage IIB : (T1-2,N1) and (T3 : > 5 cm and ≤ 7 cm in greatest dimension surrounded by lung or associated with separate tumor nodule(s) in the same lobe but **without** mediastinum or chest wall involvements, or superior sulcus tumors, N0) on the basis of clinical evaluation (8th classification TNM, UICC 2015). In case of invasion of the main bronchus (distance < 2 cm from carina), a biopsy of the carina is required. A pre-surgical PET scan of the thorax and a MRI or CT scan of the brain as well as thorax abdomen pelvis CT scan must be done prior to surgery and before inclusion. **If preoperative CT and/or PET are suspicious for mediastinal nodal involvement, invasive mediastinal staging with mediastinoscopy or EBUS-TBNA must be performed.** Station 5 or 6 lymph nodes may be accessed by anterior mediastinotomy or VATS.
- 4 Pre-operative (neo-adjuvant) platinum based or other chemotherapy except the treatment of the protocol is not permissible. Pre-operative radiation therapy is not permissible
- 5 The patient must have an ECOG performance status of 0, 1.
- 6 Hematology (done within 14 days prior to inclusion and with values within the ranges specified below):
If anemic, patients should be asymptomatic and should not be decompensated. Transfusions are permissible.

Haemoglobin ≥ 9,0 g/dL

Absolute neutrophil count ≥ $1.5 \times 10^9/L$ or ≥ 1,500/ μ l

Platelets ≥ $100 \times 10^9/L$ or ≥ 100,000/ μ l

- 7 Biochemistry (done within 14 days prior to inclusion and with values within the ranges specified below):

Total bilirubin* within normal institutional limits

Alkaline phosphatase ≤ 2.5 x institutional upper limit of normal

AST(SGOT) and ALT(SGPT) ≤ 2.5 x institutional upper limit of normal

Creatinine Clearance ≥ 40 ml/min

TSH

within normal institutional limits

* *excluding Gilbert's syndrome*

Creatinine clearance to be measured directly by 24 hour urine sampling or as calculated by Cockcroft Formula:

$$\text{Females: GFR} = \frac{1.04 \times (140 - \text{age}) \times \text{weight in kg}}{\text{serum creatinine in } \mu\text{mol/L}}$$

$$\text{Males: GFR} = \frac{1.23 \times (140 - \text{age}) \times \text{weight in kg}}{\text{serum creatinine in } \mu\text{mol/L}}$$

- 8 Other investigations detailed in Section 6 must have been performed within the timelines indicated.
- 9 Patient consent must be appropriately obtained in accordance with applicable local and regulatory requirements. Each patient must sign a consent form prior to inclusion in the trial to document their willingness to participate.
- 10 Patients must be accessible for treatment and follow-up. Investigators must assure themselves the patients included on this trial will be available for complete documentation of the treatment, adverse events, and follow-up.
- 11 Protocol treatment is to begin within 7 days of patient inclusion.
- 12 Age of at least 18 years.
- 13 Female subjects must either be of non-reproductive potential (ie, post-menopausal by history: ≥ 60 years old and no menses for ≥ 1 year without an alternative medical cause; OR history of hysterectomy, OR history of bilateral tubal ligation, OR history of bilateral oophorectomy) or must have a negative serum pregnancy test upon study entry.
- 14 Females of childbearing potential who are sexually active with a non-sterilized male partner or men who are sexually active with women of childbearing potential must use a highly effective method of contraception prior the first dose of investigational product, and must agree to continue using such precautions for 4 months after the final dose of investigational product. Periodic abstinence, the rhythm method, and the withdrawal method are not acceptable methods of contraception.

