7 PRE-TREATMENT EVALUATION

Investigations		Timing
History and Physical Exam including:	
 • history including cigarette smoking • physical examination including height, weight, pulse, blood pressure • performance status • Concomitant medication 	Within 14 days prior to inclusion
Haematology	
 • CBC including haemoglobin, differential leukocyte, platelet count 	Within 14 days prior to inclusion
Biochemistry	
 • AST (SGOT) and ALT (SGPT) • Alkaline phosphatase • Total bilirubin (if total bilirubin is $\geq 2xULN$ (and no evidence of Gilbert's syndrome) then fractionate into direct and indirect bilirubin • Gamma glutamyltransferase • albumin • creatinine • Urea • CRP • TSH¹ • INR/APTT • Lactate dehydrogenase • Uric acid • Lipase • Amylase (if lipase > 2,5N) • Magnesium • Potassium • Bicarbonate sodium • Calcium • Chloride • Total protein 	Within 14 days prior to inclusion
	
 • HIV antibody • Hepatitis A antibody, • Hepatitis B surface antigen • Hepatitis C antibody 	

Radiology	
 • baseline CT chest and upper abdomen (must include adrenal glands) ² 	Within 28 days prior to inclusion
	
 • MRI or CT of brain • PET scan 	Within 28 days prior to inclusion
	
 • other baseline imaging (e.g. bone scan) 	Required, within 28 days of inclusion, only if suspicious signs/symptoms are present
Other Investigations	
 • ECG 	Within 2 months prior to inclusion if clinically indicated
	
 • urinalysis • lung function tests: FEV1, FVC, TLCO and SaO2 on room air • pregnancy test if applicable 	Within 2 months prior to inclusion
	
 • LVEF ³ 	Within 12 weeks prior to inclusion
	
 • Serum, plasma for correlatives • Feces • Tumor block available 	Prior to Cycle 1, day 1 dosing ⁴

1 If TSH is abnormal, both T3 and T4 should be measured (both are recommended but at least one of T3 or T4 is mandatory if TSH is abnormal).

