12.5 Reporting of pregnancy

The investigator is required to report to the sponsor any pregnancy where the embryo/fetus could have been exposed to durvalumab. This means pregnancies occurring in female participants, female partners of male participants, or females exposed through direct contact with the agent during their pregnancy (for example, environmental exposure involving direct contact with the agent). Pregnancies occurring up to 90 days after the completion of durvalumab must also be reported.

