APPENDIX I - PATIENT EVALUATION FLOW SHEET

Required investigations	Pre-study	Prior to each infusion	Prior to surgery	4 weeks after surgery	6 months and one year after surgery
History	X	X		X	X
Physical exam	X	X		X	X
Smoking history	X				
ECOG	X	X		X	X
Collection of adverse events	X	X		X	X
CBC, Differential leukocyte, platelet count	X	X		X	As clinically indicated
AST, ALT, alkaline Phosphatase, bilirubin, gamma glutamyltransferase, albumin, serum creatinine, urea, lactate dehydrogenase, uric acid, lipase, amylase (if lipase > 2,5N), magnesium, potassium, bicarbonate sodium, calcium, chloride, total protein, HIV antibody ¹ , Hepatitis A antibody ¹ , Hepatitis B surface antigen ¹ , Hepatitis C antibody ¹	X	X		X	As clinically indicated
TSH ²	X	X ³		X	As clinically indicated
CRP	X	X			
INR/APTT	X	As clinically indicated			
CT chest and upper abdomen (must include adrenal glands) ³	X		X		X
CT or MRI brain	X	As clinically indicated			
PET scan thorax	X		X		
Other imaging	As clinically indicated ⁴				
ECG	X	As clinically indicated		X	As clinically indicated
Pregnancy test (if applicable)	X	As clinically indicated			
Lung function tests (FEV1, FVC, TLCO and SaO2 on room air)	X	As clinically indicated			
Urinalysis	X	As clinically indicated			
LVEF	X ⁵				
Bio-IFCT : serum, plasma	X	X ⁶			

1 Pre-study only

2 If TSH is abnormal, both T3 and T4 should be measured (both are recommended but at least one of T3 or T4 is mandatory if TSH is abnormal).

3 One month after the first infusion only

4 When relapse is first documented at any site, complete restaging is required to identify all site of relapse

5 MUGA or ECHO, only for patients with significant cardiac history.

6 3rd infusion only

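### Eligibility criterion 13 ties the negative serum pregnancy test to study entry, while the Section 7 table accepts a test up to two months before inclusion and no later test is scheduled

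*Protocol*

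**What the plan says.** The protocol deals with pregnancy testing in several places.

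- **Section 5.1, criterion 13.** A female patient is either of non-reproductive potential or "must have a negative serum pregnancy test upon study entry".
- **Section 5.1, criterion 8.** The other pre-treatment investigations "must have been performed within the timelines indicated". The criterion points to Section 6, but the table of investigations is in Section 7.
- **Section 7, pre-treatment table.** The entry reads "pregnancy test if applicable" and shares a row with urinalysis and lung function tests. The window for that row is "Within 2 months prior to inclusion". Haematology and biochemistry in the same table are due "Within 14 days prior to inclusion".
- **Section 9.1 and Appendix I.** In the Appendix I flow sheet, the row that begins "Pregnancy test (if applicable" is marked at pre-study. After that, both places leave the test to clinical indication.
- **Section 5.1, criterion 11, and Section 8.** Treatment starts within 7 days of inclusion according to the first, and within 7 working days according to the second.
- **Section 5.2, exclusion criterion 14.** Pregnant women are ineligible, as are patients of reproductive potential who are not using effective birth control.

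Two further passages concern the period after dosing. Under criterion 14 of Section 5.1, patients "must agree to continue using such precautions for 4 months after the final dose of investigational product". Section 12.5 states: "Pregnancies occurring up to 90 days after the completion of durvalumab must also be reported".

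**The concern.** A result obtained two months before inclusion is not, on an ordinary reading, a result obtained at study entry. The conflict has practical weight because sites book screening tests from the table, and criterion 8 tells them that meeting the tabulated timelines is what eligibility requires. A site can therefore believe that it has complied while criterion 13 is unmet.

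The stake is participant safety. An entry test serves to detect a pregnancy that neither the patient nor the investigator knows about. An old negative result cannot do this for a conception that came after it, and no scheduled test follows before the infusions or the operation.

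**Working it through.** The protocol gives no figure of its own for this interval. The check sets the passages side by side and adds the permitted windows.

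**Step 1: do the passages agree?**

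| Feature | Criterion 13 | Section 7 table | Section 9.1 and Appendix I |
|---|---|---|---|
| Timing | Study entry | Up to 2 months before inclusion | Pre-study (Appendix I), then only if clinically indicated |
| Test type | Serum | Not stated | Not stated |
| Scheduled repeat | None | None | None |

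The timings differ. The test type is stated in only one place. That is an omission in the table and not a contradiction, because criterion 13 supplies the type.

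**Step 2: does the table carry the force of an eligibility rule?** Yes, through criterion 8, once its reference to Section 6 is read as meaning Section 7. Criteria 8 and 13 therefore apply different standards to the same test.

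**Step 3: oldest result at inclusion under the table.** Two consecutive calendar months contain 59 to 62 days, so the result can be about 59 to 62 days old.

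**Step 4: oldest result at first dose under the table.**

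- With the 7 days of criterion 11: 59 + 7 = 66 and 62 + 7 = 69, so 66 to 69 days.
- With the 7 working days of Section 8, which span about 9 to 11 calendar days (one or two weekends): 59 + 9 = 68 and 62 + 11 = 73, so 68 to 73 days.
- Over both rules: about 66 to 73 days.

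For comparison, blood tests done 14 days before inclusion would be at most 14 + 7 = 21 days old at first dose under criterion 11, or 14 + 11 = 25 days old under Section 8.

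**Step 5: which part of that interval lacks another safeguard?** Exclusion criterion 14 makes effective birth control a condition at inclusion, and criterion 14 of Section 5.1 requires highly effective contraception before the first dose. The days from inclusion to first dose are therefore covered by a contraception requirement. The days from the test to inclusion, up to about 59 to 62, are not, because neither criterion requires contraception from the date of the test.

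**The case against.** The strongest reply is that eligibility criteria are cumulative and Section 5.1 allows no exceptions. The two-month window is an outer limit in a schedule and does not waive criterion 13. A serum test at entry satisfies both passages, and a woman with only an old test fails criterion 13. Pregnant women are excluded in any case. Study entry is also undefined. If it means the screening period, the contradiction shrinks to a question of window length.

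Much of this stands. A reader might infer that the protocol permits a pregnant woman to be included and dosed. It does not: a known pregnancy excludes her, and criterion 13 still binds. What survives is that the schedule and the criterion give sites different instructions, that criterion 8 lends authority to the looser one, and that no scheduled test would reveal the error. Reading study entry as the whole screening period does not help much, because it would leave criterion 13 satisfied by a result of about two months.

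Three other inferences are tempting and are not supported.

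- **A breach of criterion 13 would affect the primary analysis.** Section 15.3 removes only patients with deviations judged major on review. Nothing says that an old pregnancy test would be judged major, and few patients are concerned.
- **The whole interval from test to dose lacks contraception cover.** From inclusion onward, exclusion criterion 14 applies.
- **Pregnancies between 90 days and 4 months after the last dose go unreported.** The first sentence of Section 12.5 requires a report of any pregnancy with possible exposure of the embryo or fetus and sets no time limit. The 90-day sentence adds to that duty and does not cap it. The two periods differ, but the difference does not establish a gap in reporting.

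**Conclusion.** The inconsistency is real and should be corrected. Criterion 13 and the Section 7 table set different timings for the same test, and no later scheduled test closes the difference. A site following the table could rely on a result about 59 to 62 days old at inclusion and about 66 to 73 days old at first dose. These figures assume that the full windows are used and that criterion 8 is meant to refer to the Section 7 table.

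The remaining risk is narrow: a conception after the test that is undetected at inclusion. The protocol does not give the number of women of childbearing potential expected. The assumption here is that it is small in an early-stage lung cancer population. The argument for acting is the seriousness of a single case and the very low cost of the correction. The difference between 90 days and 4 months is a minor point of harmonisation.

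**What to change.** 1. In Section 7, take the pregnancy test out of the two-month group and give it its own row, so that its timing and test type match criterion 13. Align the Appendix I entry. The sponsor should define study entry and set the exact window.
2. Correct the cross-reference in criterion 8 so that it points to the section holding the table.
3. Reconcile the 7 days in criterion 11 with the 7 working days in Section 8, since both determine the age of the result at first dose.
4. As a minor point, reconcile the 90 days in Section 12.5 with the 4-month contraception period in criterion 14, keeping the open-ended duty in the first sentence of 12.5.

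The cost is wording: one row in each of two tables, two criteria or their counterparts, and one sentence in Section 12.5. Criterion 13 already requires the test, so no new procedure is added.

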5.2 Ineligibility Criteria

Patients who fulfil any of the following criteria are not eligible for admission to the study:

- 1 Patients with a history of other malignancies, except: adequately treated non-melanoma skin cancer, curatively treated in-situ cancer, or other solid tumours curatively treated with no evidence of disease for ≥ 5 years following the end of treatment and which, in the opinion of the treating physician, do not have a substantial risk of recurrence of the prior malignancy.
- 2 A combination of small cell and non-small cell lung cancer or pulmonary carcinoid tumour.
- 3 History of autoimmune disease, including but not limited to myasthenia gravis, myositis, autoimmune hepatitis, systemic lupus erythematosus, rheumatoid arthritis, inflammatory bowel disease, vascular thrombosis associated with antiphospholipid syndrome, Wegener's granulomatosis, Sjögren's syndrome, Guillain-Barré syndrome, multiple sclerosis, vasculitis, or glomerulonephritis. NOTE: patients with Grave's disease and/or psoriasis not requiring systemic therapy within the last two years from inclusion are not excluded.

4 History of primary immunodeficiency, history of allogenic organ transplant, use of immunosuppressive agents within 28 days of inclusion* or a prior history of severe (grade 3 or 4) immune mediated toxicity from other immune therapy.

* *NOTE: Intranasal/inhaled corticosteroids or systemic steroids that do not to exceed 10 mg/day of prednisone or equivalent dose of an alternative corticosteroid are permissible.*

5 Live attenuated vaccination administered within 30 days prior to inclusion.

6 History of hypersensitivity to durvalumab or any excipient.

7 Patients who have experienced untreated and/or uncontrolled cardiovascular conditions and/or have symptomatic cardiac dysfunction (unstable angina, congestive heart failure, myocardial infarction within the previous year or cardiac ventricular arrhythmias requiring medication, history of 2nd or 3rd degree atrioventricular conduction defects). Patients with a significant cardiac history, even if controlled, should have a LVEF > 50% within 12 weeks prior to inclusion.

8 Concurrent treatment with other investigational drugs or anti-cancer therapy.

9 Patients with active or uncontrolled infections or with serious illnesses or medical conditions which would not permit the patient to be managed according to the protocol. This includes but is not limited to:

- known prior history of tuberculosis;
- known acute hepatitis B or C by serological evaluation;
- known Human immunodeficiency virus infection.

10 Current or prior use of immunosuppressive medication within 28 days before the first dose of durvalumab, with the exceptions of intranasal and inhaled corticosteroids or systemic corticosteroids at physiological doses, which are not to exceed 10 mg/day of prednisone, or an equivalent corticosteroid

11 Any previous treatment with a PD1 or PD-L1 inhibitor, including durvalumab

12 Active or prior documented inflammatory bowel disease (e.g., Crohn's disease, ulcerative colitis)

13 Known history of previous clinical diagnosis of tuberculosis

14 Female subjects who are pregnant, breast-feeding or male or female patients of reproductive potential who are not employing an effective method of birth control

15 Any condition that, in the opinion of the investigator, would interfere with evaluation of study treatment or interpretation of patient safety or study results

